12.2 Monitoring for Adverse Events

At each visit, after the subject has had the opportunity to spontaneously mention any problems, the Investigator should inquire about AEs by asking the standard questions:

- “Have you had any health problems since the last study visit?”
- “Have there been any changes in the medicines you take since the last study visit?”

AEs should be reported for any clinically relevant change in concomitant medication(s) that is the result of an untoward (unfavorable and unintended) change in a subject’s medical health.

Changes in any protocol specific parameters and questionnaires (if applicable) evaluated during the study are to be reviewed by the Investigator. Any untoward (unfavorable and unintended) change in a protocol specific parameter or questionnaire response that is clinically relevant is to be reported as an AE. These clinically relevant changes will be reported regardless of causality.

12.3 Procedures for Recording and Reporting

Subsequent to signing an informed consent form, all untoward medical occurrences that occur during the course of the study must be documented on an Adverse Event Form (AEF). A separate AEF must be filed out for each event. When possible, signs and symptoms

indicating a common underlying pathology should be documented as one comprehensive event. For each recorded event, the AE documentation must include the onset date, outcome, resolution date (if event is resolved), intensity, (ie, severity), any action with study product taken as a result of the event, and an assessment of the AE's relationship to the study product.

Reporting Serious Adverse Events

All available information on SAE(s) and any other associated AE, if applicable, must be forwarded to the study Sponsor immediately (ie, within 24 hours of the Investigator's or site's knowledge of the event) as follows: In studies utilizing EDC, all available information for the SAE and any associated AE(s) must be entered immediately into the EDC system.

NOTE: Should the EDC system become non-operational, the site must complete the appropriate paper Serious Adverse Event Form. The completed form is communicated to the study Sponsor either by fax at [REDACTED] or by email at [REDACTED] within 24 hours of the Investigator's or site's awareness, however, the reported information must be entered into the EDC system once it becomes operational.

Additional information for any applicable event is to be reported as soon as it becomes available. Any complaints from the subject on a past event previous to initiation of the study but that is resolved at the time of the first visit must be reported to Alcon following the usual pharmacovigilance circuit.

Reporting Quality Complaints

Any malfunction or quality complaint, which occurs during this study must be reported within 10 calendar days via data entry within the clinical study EDC system or by fax to the Sponsor in the event that electronic data entry is not possible. See the MOP for the list of Study Staff personnel to contact.

The Investigator will be asked to determine whether they believe the study product was associated with, or contributed to, the event. This information is to be documented via data entry within the clinical study EDC system.

The Sponsor's Medical Safety Department is responsible for archiving and submitting all reportable quality complaints and AEs to the appropriate regulatory authorities.

12.4 Intensity and Causality Assessments

For every AE, the Investigator must assess the seriousness, intensity (severity) and causality (relationship to study product). Specifically, events should be classified as mild, moderate, or severe. The assessment of causality will be based upon the categories of related and not related. An assessment of causality will also be performed by Sponsor physician utilizing the same definitions. These classifications should be based on the following definitions:

Intensity (Severity):

- Mild An event is mild if the subject is aware of, but can easily tolerate the sign or symptom.
- Moderate An event is moderate if the sign or symptom results in discomfort significant enough to cause interference with the subject's usual activities.
- Severe An event is severe if the sign or symptom is incapacitating and results in the subject's inability to work or engage in their usual activities.

Causality:

- Related An AE considered related to the use of the study product.

Adverse events classified as related may be either definitely related or possibly related where a direct cause and effect relationship between the study product and the event has not been demonstrated but there is a reasonable possibility that the event was caused by the study product.

- Not Related An AE considered unrelated to the use of the study product. Adverse events classified as not related may either be definitely unrelated or simply unlikely to be related (ie, there are other more likely causes for the AE).

For a SAE reported by an Investigator as not related that upon review of the available data by the Sponsor physician is assessed (upgraded) to be related, the Investigator will receive a notification.

12.5 Unmasking of the Study Information

Masked information on the identity of the assigned study product should not be disclosed during the study. If the treatment code needs to be broken in the interest of subject safety, the Investigator is encouraged to contact an appropriate Sponsor representative prior to unmasking the information if there is sufficient time. Depending upon the individual

circumstances (ie, medical emergency), the code may be broken prior to contact with the Sponsor. The Sponsor must be informed in all cases in which the code was broken and of the circumstances involved. Additionally, the Sponsor may be required to unmask the information in order to fulfill expedited regulatory reporting requirements.

12.6 Follow-Up of Safety Information

The Investigator is responsible for adequate and safe medical care of subjects during the study and for ensuring that appropriate medical care and relevant follow-up procedures are maintained after the study. Any additional data from these follow-up procedures must be documented and available to the Sponsor who will determine when the data need to be documented on the case report forms.

12.7 Pregnancy in the Clinical Study

Women who are pregnant or breast-feeding are excluded from participation in the study. Women of childbearing potential or women considered post-menopausal are not excluded from the study as long as adequate birth control methods are being utilized. All women of childbearing potential are required to use adequate birth control methods which are summarized in the protocol's exclusion criteria.

Prior to clinical study enrollment, female subjects of childbearing potential must be advised of the importance of avoiding pregnancy during the study and the potential risks associated with an unintentional pregnancy. During the study, female subjects are to be instructed to contact the Investigator immediately if they suspect they might be pregnant. Sponsor must be contacted immediately, treatment discontinued, and the subject exited from the study.

In addition, complications of pregnancy may be reportable and will be decided on a case by case basis. A Sponsor prepared form will be utilized to capture all pregnancy related information until the outcome of the pregnancy.

13 DATA HANDLING AND ADMINISTRATIVE REQUIREMENTS

13.1 Completion of Source Documents and Case Report Forms

The nature and location of all source documents will be identified to ensure that original data required to complete the CRFs exist and are accessible for verification by the site monitor. If electronic records are maintained, the method of verification must be determined in advance of starting the study.

At a minimum, source documents should include the following information for each subject:

- Subject identification (name, sex, race/ethnicity)
- Documentation of subject eligibility
- Date of informed consent
- Dates of visits
- Documentation that protocol specific procedures were performed
- Results of study parameters, as required by the protocol
- Study medication accountability records
- Documentation of AEs and other safety parameters (if applicable)
- Records regarding medical histories and the use of concomitant therapies prior to and during the study
- Date of study completion and reason for early discontinuation, if applicable

It is required that the author of an entry in the source documents be identifiable. Direct access to source documentation (medical records) must be allowed for the purpose of verifying that the data recorded on the CRF are consistent with the original source data.

Case report forms will be provided to the sites (electronic); only designated individuals may complete the CRFs. The CRFs will be submitted at regular intervals based upon the clinical study visit schedule. It is expected that all data reported will have corresponding entries in the source documents and that the Principal Investigator will review the reported data and certify that the CRFs are accurate and complete. No subject identifiers should be recorded on the CRFs beyond subject number, and demographic information.

13.2 Data Review and Clarifications

The CRF data will be reviewed against the subject's source data by the study monitors to ensure completeness and accuracy. After monitoring has occurred at the clinical sites and the CRFs have been submitted, additional data clarifications and/or additions may be needed. Data clarifications and/or additions are documented and are part of each subject's CRFs.

Short Title:

**Statistical Analysis Plan
EXB107-P001 / NCT02776670**

Full Title:

**Statistical Analysis Plan
EXB107-P001**

Protocol Title: Clinical evaluation following use of SYSTANE® BALANCE
in subjects with lipid-deficient dry eye

Project Number: EXB107-P001

Protocol TDOC Number: TDOC-0051783

Author: [REDACTED] MSc

[REDACTED] (NBS Dublin)

Template Version: Version 4.0, approved 16MAR2015

Approvals: See last page for electronic approvals.

Job Notes:

This is the second amended Statistical Analysis Plan (Version 3.0) for this study. This version of the Statistical Analysis Plan is based on the following: Version 4.0 of the study protocol and Version 1.0 of the UK country specific study protocol.

Executive Summary:

Key Objectives:

This study is designed to evaluate the efficacy and safety of SYSTANE[®] BALANCE in subjects with lipid-deficient dry eye after 35 days of 4 times daily (QID) treatment.

Decision Criteria for Study Success:

Evidence of efficacy will be deemed established if the lower limit of the 95% 2-sided confidence interval (CI) (equivalent to the 1-sided 97.5% CI) of the adjusted estimate of the difference (SYSTANE BALANCE - REFRESH OPTIVE[®] Advanced/ OPTIVE[®] PLUS [UK]) in mean change from baseline in tear film break-up time (TFBUT) (seconds) between SYSTANE BALANCE and REFRESH OPTIVE Advanced/ OPTIVE PLUS (UK) at Day 35 (Visit 3) in the analysis eye is above the non-inferiority margin of -1.0 second.

Table of Contents

Statistical Analysis Plan EXB107-P001 1

Table of Contents 3

List of Tables..... 4

List of Figure 5

List of Abbreviations 6

1 Study Objectives and Design..... 8

1.1 Study Objectives..... 8

1.2 Study Description..... 9

1.3 Randomization..... 10

1.4 Masking..... 10

1.5 Interim Analysis 11

2 Data Analysis General Information 11

2.1 General definitions 12

2.2 Definition of baseline date 12

2.3 Baseline and post-baseline definitions 12

2.4 Visit windowing 13

2.4.1 Early exit visits..... 13

2.4.2 Unscheduled visits..... 13

3 Analysis Sets..... 14

4 Subject Characteristics and Study Conduct Summaries..... 15

4.1 Subject disposition 15

4.2 Background and demographic characteristics 15

4.3 Medical history..... 16

4.4 Prior and concomitant medications 17

5 Efficacy Analysis Strategy..... 18

5.1 Efficacy Endpoints 18

5.2 Efficacy Hypotheses..... 19

5.3 Statistical Methods for Efficacy Analyses..... 20

5.3.1 Multiplicity Strategy..... 23

1 Study Objectives and Design

This statistical analysis plan (SAP) describes the statistical analysis planned in Section 11 of the study protocol (Clinical Trial Protocol Version 4.0) and the UK country specific study protocol (UK Clinical Trial Protocol Version 1.0) along with any additional analyses, specifications or deviations from the protocol planned before unmasking of the data.

Determination of the sample size is specified in Section 0.

This document is written in the future tense. It will be reviewed and updated (including conversion to past tense) for entry into the clinical study report (CSR) after the analysis has taken place.

The data will be analyzed by Novartis Product Lifecycle Services (PLS). Any data analysis carried out independently by the investigator should be submitted to Alcon before publication or presentation.

[figure not shown]
1.1 Study Objectives

[figure not shown]
The primary objective of the study is:

- To demonstrate that SYSTANE BALANCE is non-inferior to REFRESH OPTIVE Advanced/ OPTIVE PLUS (UK) using tear film break-up time (TFBUT) after 35 days of four times a day (QID) dosing in subjects with lipid-deficient dry eye.

The secondary objectives are:

- To demonstrate that SYSTANE BALANCE is superior to REFRESH OPTIVE Advanced/ OPTIVE PLUS (UK) using TFBUT after 35 days of QID dosing in subjects with lipid-deficient dry eye.
- To evaluate changes in Global Ocular Discomfort using a visual analog scale (VAS) following use of SYSTANE BALANCE versus REFRESH OPTIVE Advanced/ OPTIVE PLUS (UK) after 35 days of QID dosing in subjects with lipid-deficient dry eye.

[figure not shown]
1.2 Study Description

This is a phase IV, multicenter, prospective, double-masked, randomized, parallel-group study. The study will enroll subjects with lipid-deficient dry eye who meet the protocol eligibility criteria. The expected duration of subject participation in the study is approximately 7 weeks (49 days) with 4 planned study visits (including Screening Visit). The main objective is to assess the efficacy and safety of SYSTANE BALANCE in subjects with lipid-deficient dry eye.

The study involves a Saline run-in period (ranging from 7 to 14 days prior to the Baseline Visit/ Visit 1) followed by a 35-day study treatment period (see Figure 1-1). The visits are as follows:

- Screening Visit (Day -14 to Day -7)
- Visit 1 (Day 0/ Baseline)
- Visit 2 (Day 15 \pm 3)
- Visit 3 (Day 35/ End of Treatment \pm 3)

Figure 1-1 Study design

1.3 Randomization

The randomization scheme will be generated and maintained by the Sponsor’s (or designee) unmasked personnel who are not involved in the conduct or analysis of the study. Randomization will be implemented in an Interactive Response Technology (IRT) system. The randomization will be stratified by study site to ensure a balance of study treatment allocations within each investigational site. Randomization will be in a 1:1 ratio.

1.4 Masking

This study has an open-label run-in phase and a double-masked study treatment phase. The investigators, subjects and all Alcon/ Novartis personnel involved with the planning, execution and analysis of the study will be masked with regard to study treatment assignment while the study is in progress. However, there will be at least 1 designated person from each clinical site who will be unmasked. This person will be responsible for dispensing, reclaiming, conducting inventory, and will be available to address any study product irregularities.

Masking will be maintained by providing all study medications in identical packaging and labeling.

1.5 Interim Analysis

No interim analyses are planned for this study.

2 Data Analysis General Information

All analyses will be performed using SAS[®] statistical software (Version 9.4 or a more recent version), unless otherwise noted.

Assessments documented in the database that occur as “bilateral” (i.e. both eyes [OU]) will be summarized and listed for each eye separately. To facilitate derivations and analysis based on eye, database records for bilateral will be split into two records containing identical information as the original record with the exception of the laterality which shall be recoded to “Right” (i.e. right eye [OD]) and “Left” (i.e. left eye [OS]), respectively. It should be noted that dependent on the assessment and at the discretion of the medical team, the assessment may only be counted once.

Data will be summarized with respect to demographic and baseline characteristics, primary, secondary, and [REDACTED], along with safety observations.

Descriptive statistics (the number of non-missing observations, mean, median, standard deviation [SD], lower quartile [Q1], upper quartile [Q3], minimum and maximum values) will be presented for continuous variables. The following number of decimal places will be used: mean, median, Q1 and Q3 values to 1 more decimal place than the raw data; minimum and maximum to the same number of decimal places as the raw data and SD to 2 more decimal places than the raw data.

For categorical variables, the number and percentage of each category within a variable will be calculated for non-missing data. If a count of zero is obtained for categorical data, the zero count and percentage will still be displayed. If no treatment satisfies a category, then the category will still be displayed, with the exception of the protocol deviations (PDs) summary. A row (category) denoted “Missing” will be included in count tabulations if a non-zero count of missing values is present for any of the treatment groups. In addition, the corresponding percentage for this row will be displayed.

Change from baseline will only be summarized for subjects with both baseline and post-baseline data for the relevant visit and will be calculated as:

$$\text{Change from baseline} = \text{Post-baseline value} - \text{baseline value}$$

Unless otherwise specified, all statistical tests will be two-sided and performed using a 5% significance level, leading to 95% (two-sided) confidence intervals (CIs). If a CI is presented for the proportion of a categorical variable, then the exact Clopper-Pearson method will be used to calculate the 2-sided 95% CI.

All data will be listed by subject and eye, unless stated otherwise.

2.1 General definitions

All analyses will be based on assessments according to the investigator, with the exception of the subject reported outcomes (VAS, [REDACTED] questionnaire). This study will consist of the following epochs:

- a screening period
- a study treatment period

Study treatment refers to:

- SYSTANE BALANCE
- REFRESH OPTIVE Advanced/ OPTIVE PLUS (UK)

For efficacy analyses, the study eye will be the worst eye at baseline for each parameter. If the baseline values are equivalent, the right eye will be selected. For safety analyses, the study eye will be selected as the eye with the worst change from baseline to any visit (scheduled or unscheduled). If both eyes have the same level of worsening, the right eye will be selected. A subject may have a different study eye for each parameter of interest, henceforth this eye will be referred to as the analysis eye.

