The study eye will be the worst eye at baseline for each parameter. If the baseline values are equivalent, the right eye will be selected.

The analysis of the primary efficacy parameter, change from baseline in TFBUT at Day 35 in the study eye, will be based on a mixed model. The mixed model will include terms for baseline TFBUT, treatment, visit (Day 15, Day 35), and treatment-by-visit interaction. Estimates of the difference (SYSTANE BALANCE - REFRESH OPTIVE Advanced) in mean change from baseline in TFBUT between SYSTANE BALANCE and REFRESH OPTIVE Advanced and associated 95% confidence interval (CI) will be presented. Evidence of noninferiority will be deemed established if the lower limit of the 95% CI for the difference is above -1.0.

The analysis of the secondary efficacy parameter LLT AUC₁₂₀ at Day 35, change from baseline in Global Ocular Discomfort VAS score at Day 35, and change from baseline in TFBUT at Day 35 will be based on a mixed model. The mixed model will include terms for baseline parameter value, treatment, visit (Day 15, Day 35), and treatment-by-visit interaction. Estimates of the difference in mean change from baseline between SYSTANE BALANCE and REFRESH OPTIVE Advanced and associated 95% CI will be presented. The primary endpoint (ie, change from baseline in TFBUT at Day 35) and both secondary endpoints will be evaluated for superiority of SYSTANE BALANCE over REFRESH OPTIVE Advanced.

[REDACTED]

The mixed model will include terms for baseline parameter value and treatment. Estimates of the difference in mean change from baseline between SYSTANE BALANCE and REFRESH OPTIVE Advanced and associated 95% CI will be presented.

[REDACTED]

To ensure overall control of the type I error rate, the secondary efficacy hypotheses will be relevant only if the primary efficacy null hypothesis is first rejected at the 5% level of significance (2-sided). Following the rejection of the primary efficacy null hypothesis, the secondary hypotheses will be tested following the Hochberg testing

Sponsor: Alcon Research, Ltd.
[name]
[name]

Protocol Number: EXB107-P001

procedure.

Safety:

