9 TREATMENTS ADMINISTERED

Subjects who meet the eligibility criteria will first be dispensed Preservative-Free Saline to be used during the run-in period between the Screening Visit and Visit 1 (Baseline/ Day 0).

At Visit 1, subjects who meet the eligibility criteria (as determined by the re-evaluation of the TFBUT assessment prior to randomization) will be randomized in a 1:1 manner to receive treatment with SYSTANE BALANCE Lubricant Eye Drops or REFRESH OPTIVE Advanced Lubricant Eye Drops. Throughout the study, the Investigator will be responsible for the accounting of all study materials and will ensure that the study products are not used in an unauthorized manner.

This study is double-masked. Designated unmasked individual(s) at each site must be assigned to dispense and reclaim the masked study product. Unmasked individuals should not be involved in conducting any subject assessments. Extreme caution should be used to avoid potential unmasking of the individuals conducting subject assessments.

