10.2.2.1 Randomization, Visit 1 (Day 0/ Baseline)

1. Obtain information on any changes in medical health and/or the use of concomitant medications.
2. The site staff will perform accountability, record, and collect the number of used and unused containers of Saline.
3. Subjects should complete the following questionnaires:
 - 
 - Ocular Discomfort questionnaire
4. The following assessments must be completed OU (see the MOP for details regarding each assessment and the order of testing).

- BCVA must be measured using an ETDRS or Tumbling E chart at a distance of 3 or 4 meters using the letters read method. The test may be performed using the subject's historical correction. Visual acuity testing should precede any examination requiring diagnostic drops (eg. dilating drops) or contact with the eye. BCVA must be ≥ 55 in both eyes for the subject to qualify for the study.
 - Slit-lamp examination
 - LLT assessments
 - TFBUT OD \times 3, OS \times 3
 - 
5. Re-confirm subject eligibility. Eligible subjects must have a TFBUT (sum of 3 measures \leq 15 seconds at Screening and baseline in the same eye(s)), and BCVA (≥ 55 letters in each eye at Screening and baseline). The qualifying eye with the shorter mean TFBUT at baseline would be the study eye. The same study eye must also have qualified at Screening.
 6. If the subject does not qualify, the visit should stop and the subject should be exited from the study as a screen failure.
 7. If the subject qualifies, randomize the subject and obtain the masked study product kit number(s) to be dispensed. The unmasked site staff will retrieve and dispense the assigned masked study product kit(s).
 8. The unmasked site staff will instill a single drop of the masked test/control product that was dispensed to the subject in each eye. Masked site personnel must not be present while the bottle of masked test/control product is removed from the kit and administered.
 9. Subjects will be instructed to dose 1 drop of the test/control product in each eye QID. The last dose should be at bedtime (ie, no later than midnight).
 10. Subjects will be instructed to retain and return all used and unused kits at their next visit.
 11. Record any AEs that are observed or reported, including those associated with changes in concomitant medication dosing.
 12. Schedule Visit 2 to take place 15 ± 3 days after Visit 1.

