11.4.1.2 Analysis Methods

The primary efficacy analysis population will be the PPS.

The analysis of the primary efficacy parameter, change from baseline in TFBUT at Day 35 in the study eye, will be based on a mixed model repeated measures (MMRM) analysis. The mixed model will include terms for baseline TFBUT, treatment (SYSTANE BALANCE,

REFRESH OPTIVE Advanced), visit (Day 15, Day 35), and treatment-by-visit interaction. The response variable is the change from baseline in TFBUT for the study eye.

An unstructured variance-covariance matrix will be used to model the within-subject correlation. If the unstructured variance-covariance matrix results in a lack of convergence then other covariance structures will be investigated.

Within-treatment and estimates of the difference (SYSTANE BALANCE – REFRESH OPTIVE Advanced) in mean change from baseline in TFBUT between SYSTANE BALANCE and REFRESH OPTIVE Advanced and associated 95% CI will be presented. Evidence of noninferiority will be deemed established if the lower limit of the 95% CI for the difference is above -1.0.

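### Do the two descriptions of the study eye leave the primary TFBUT endpoint undefined?

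*SAP*

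**What the plan says.** The visit procedure and the analysis sections describe the eye differently.

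- **Protocol 10.2.2.1, step 5 (Visit 1).** Eligibility is re-confirmed on a three-reading TFBUT sum of at most "15 seconds at Screening and baseline in the same eye(s"), and on BCVA in each eye. The step then says "The qualifying eye with the shorter mean TFBUT at baseline would be the study eye", and adds "The same study eye must also have qualified at Screening". It gives no rule for ties.
- **Protocol synopsis (Planned Analyses) and protocol 11.4.** Both say "The study eye will be the worst eye at baseline for each parameter", with the right eye taken when the baseline values are equal. Neither mentions qualification.
- **Protocol 11.4.1.2 (primary model).** "The response variable is the change from baseline in TFBUT for the study eye".
- **SAP 2.1.** "For efficacy analyses, the study eye will be the worst eye at baseline for each parameter", with the same tie rule. The eye may differ between parameters, and "henceforth this eye will be referred to as the analysis eye".
- **SAP Executive Summary, 5.1, 5.2, 5.3 and 9.** The success criterion, TFBUT endpoint, hypotheses, primary MMRM and power statement all refer to the analysis eye.

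Inclusion criterion 3 is met if at least one eye satisfies both the TFBUT and the Schirmer condition. Protocol 9 describes Visit 1 eligibility "as determined by the re-evaluation of the TFBUT assessment prior to randomization", and the schedule of assessments places Schirmer at Screening only.

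**The concern.** Within the protocol one term carries two meanings, and the primary response is measured in the eye that the term names. Because one qualifying eye is enough for entry, a subject's worse eye at Visit 1 can be one that failed a Screening condition. The worst-eye rule takes that eye; step 5 excludes it. Nothing in either document says that step 5 is set aside for analysis. SAP 11.1, which lists changes to protocol-specified analyses, records only the LLT decision.

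If the analysis really were open, someone could choose between two documented eye rules for the only primary endpoint, in a noninferiority trial with about 80% power. With an estimate near the decision boundary, that choice could change the verdict.

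**Working it through.** **1. Which rule governs the analysis?** Protocol 11.4.1.2 is a subsection of 11.4, and 11.4 opens by defining the study eye as the worst eye at baseline. That definition controls the term in its own subsection ahead of an eligibility step in section 10. SAP 2.1 limits its rule to efficacy analyses and renames the eye, and every later SAP statement about the primary endpoint uses the new name. SAP 1 says the document implements protocol section 11. That section already specifies the worst eye, so the SAP changed nothing here that 11.1 had to record.

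**2. When can the rules disagree?** With three readings per eye, a sum of at most 15 s is a mean of at most 5 s. If the worse eye at Visit 1 had a mean above 5 s, so would the better eye, and the subject could not be enrolled. The Visit 1 cut therefore never separates the rules. Apart from ties, they differ only when the worse Visit 1 eye failed a condition at Screening: TFBUT, or Schirmer if qualifying is read to include it. BCVA is required in each eye and cannot separate them.

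**3. How often?** The documents give only a mean baseline TFBUT of about 4 s (protocol 11.4.1.1), so frequency has to be assumed. Two simulations with different assumptions gave these shares of enrolled subjects:

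| Simulation (assumed inputs) | TFBUT only | Schirmer also counted |
|---|---|---|
| 972 scenarios: log-normal TFBUT, median 3.5–5 s, log-SD 0.25–0.5, inter-eye correlation 0.5–0.95, between-visit correlation 0.5–0.9; log-normal Schirmer, median 7 or 10 mm | 0.1%–6.9%, median 1.4% | 1.1%–19.7%, median 8.1% |
| 18 scenarios: log-normal TFBUT, median 4 s, log-SD 0.4, inter-eye correlation 0.5–0.9, between-visit correlation 0.5–0.7; 50%–95% of eyes within the Schirmer range | 1.1%–5.0% | 4.5%–26.4% |

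Of 220 randomized, 1.4% is about 3 subjects, 6.9% about 15, 8.1% about 18 and 26.4% about 58.

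**4. What would it do to the estimate?** Inputs from protocol 11.10: SD 2.5, 100 evaluable per arm, true difference 0, margin 1.0 s, one-sided 0.025.

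- Standard error = 2.5 × √(2/100) = 0.354 s.
- Noninferiority is met when the estimate exceeds −1 + 1.96 × 0.3536 = −0.307 s.
- Power = Φ(0.307/0.3536) = 80.7% by normal approximation (80.4% by noncentral t), which reproduces the plan's figure of about 80%.

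Let a share f of subjects switch eye, and let the two eyes' changes correlate ρ (assumed 0.5 or 0.7) with the same treatment effect. Ignoring baseline adjustment:

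- SD of the shift = √(f × 2 × 2.5² × (1 − ρ) × 2/100).
- Correlation of the two estimates = 1 − f(1 − ρ). The bivariate normal then gives the chance that the two verdicts differ.

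| f | SD of shift (s), ρ = 0.5 / 0.7 | Verdicts differ, ρ = 0.5 / 0.7 |
|---|---|---|
| 1.4% | 0.042 / 0.032 | 2.6% / 2.0% |
| 6.9% | 0.093 / 0.072 | 5.7% / 4.4% |
| 8.1% | 0.101 / 0.078 | 6.2% / 4.8% |
| 26.4% | 0.182 / 0.141 | 11.3% / 8.7% |

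**5. What the last column means.** It is the chance that two valid analyses, run on partly different eyes, fall on opposite sides of −0.307 s. It is not an error rate. With one rule fixed in advance and chosen from pre-dose values, the type I error of the planned test is unaffected.

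**The case for a change.** The strongest case for a change is that this is the sole primary endpoint, that step 5 is still live protocol text, and that the SAP says it describes deviations from the protocol yet never mentions dropping the qualifying condition. The word qualifying is also unsettled. Criterion 3 lists Schirmer at both visits, Schirmer is measured only at Screening, and step 5 re-confirms TFBUT and BCVA only. On the Schirmer reading the share affected need not be trivial. A superseding sentence and one sensitivity run would use data already collected, and SAP 11.1 says the database is not locked and the code is unbroken.

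Part of this stands. The wording is inconsistent, it has not been reconciled, and an eye that failed a Screening condition can supply the primary endpoint.

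The rest does not amount to a defect in the analysis. Step 5 is a site procedure for confirming eligibility, while the sections that specify the analysis agree with one another. Criterion 3 is met by the subject, not by each eye, so using the worst eye breaches no entry rule. The sentence in step 5 just before the study-eye wording ties qualification to TFBUT, which favours the lower frequencies. A superseding sentence would leave every number the SAP produces unchanged, and a run in the qualifying eye would answer a slightly different question without correcting a wrong answer.

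**Conclusion.** The concern does not call for a change. There is a real but minor wording inconsistency between protocol 10.2.2.1 and the analysis sections. An analyst following the SAP has one rule for the primary endpoint: the worst eye at baseline, right eye if tied, chosen before dosing. That rule is legitimate, introduces no treatment bias, and leaves the sample size and the noninferiority test as planned.

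How many subjects the two descriptions would separate cannot be derived from the documents. Under the assumptions above it is probably a few of 220 if qualifying means TFBUT only, with a typical shift of 0.03 to 0.04 s against a standard error of 0.354 s and a margin of 1.0 s. It could reach tens of subjects if Schirmer is included. These sizes depend on assumed distributions and correlations. The conclusion does not, because the plan already fixes which eye is analysed.
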